6.0 Randomization and Blinding

Per Amendment 6, 26 subjects will be enrolled into the study. The randomized portion of the study will be blinded and there will be a 12:9:5 ratio between subjects in the active dose 1, active dose 2, and comparator dose treatment groups. Subjects will be assigned subject numbers, and subjects will be randomized in a blinded fashion.

7.0 Sample Size and Power Considerations

This study is a pilot investigation intended to gather preliminary data on the safety and efficacy of MDMA in 26 subjects with chronic, treatment-resistant PTSD. Because of their exploratory nature, pilot studies are often not powered for detecting the desired effect. Because it is a pilot study in a small sample, results will be used to collect effect size estimates for statistical power calculations for adequately powered subsequent studies.

8.0 Measures

8.1 Outcome Measures

Clinician-Administered PTSD Scale (CAPS-4) Global Severity Score, Diagnostic Criteria Met score, Associated Features

PTSD Diagnostic Scale (PDS), total score

Global Assessment of Functioning (GAF), total score

Beck Depression Inventory-II (BDI-II), total score

Post Traumatic Growth Inventory (PTGI), total score

Dissociative Experiences Scale-II (DES-II), total score

Pittsburgh Sleep Quality Index (PSQI), total score

States of Consciousness Questionnaire (SOCQ), total and composite scores

Long-term Follow-up Questionnaire (LTFU Questionnaire)

8.2 Safety Measures

Columbia Suicide Severity Rating Scale (C-SSRS)

Paced Auditory Serial Addition Test (PASAT)

Repeatable Battery for the Assessment of Neuropsychological Status (RBANS)

Subjective Units of Distress (SUD)

General Well-being (GWB)

Visual analog scale for Tinnitus and/or Pain visual analog scale

Vital signs (systolic blood pressure (SBP), diastolic blood pressure (DBP), heart rate (HR), body temperature (BT))

Adverse Events (AE), including Spontaneously Reported Reactions (SRR)

8.3 Process Measures

Therapist Adherence Criteria

Belief of Condition Assignment

Subject perceptions of experimental sessions

Reactions to Research Participation Questionnaire (RRPQ)

Qualitative Interviews

9.0 Analyses

In general, nominal variables will be described in terms of frequencies and percentages and analyzed using chi square analysis. Ordinal and non-normal continuous variables will be described using sample median and range, and analyzed by non-parametric statistical tests, and approximately normal variables will be described using sample mean and standard deviations and analyzed by parametric statistical tests. All statistical tests will be two-sided and a difference resulting in a p-value of less than or equal to 0.05 will be considered statistically significant. All p-values will be rounded to and displayed in four decimals. If a p-value less than 0.0001 occurs it will be shown in tables as <0.0001. For any analysis that is called out as parametric, e.g. t-test, the parametric assumptions will be examined. If necessary, nonparametric analyses will be utilized, e.g. Wilcoxon rank-sum test.

Clinical data will be presented in tabular format. Data not subject to analysis according to this plan will not appear in any tables or graphs, but will be included in the data listings. Analyses will be carried out with SAS Version 9.3 or higher. Selected results may be presented graphically using standard graphical software.

Post-hoc exploratory analyses not identified in this SAP may be performed to further examine the study data. These analyses will be clearly identified as such in the final clinical study report.

9.1 Analysis Populations

Modified Intent-to-treat (mITT): all subjects who were randomized, received at least one experimental session and completed at least one outcome assessment

Per protocol (PP): all subjects who completed two experimental sessions and primary outcome assessment in Stage 1 and did not experience a major protocol deviation

Crossover: all subjects who completed Stage 2 in addition to completing Stage 1

Safety: all subjects who receive any study treatment

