SUD		✓ ^{D,E}		✓ ^{D,E}			✓ ^{D,E}			
Overnight Stay, SOCQ		✓		✓			✓			
Integrative Therapy Session			✓ ^A		✓ ^A			✓ ^A		
Seven Days Telephone Contact			✓		✓			✓		
AEs Requiring Medical Attention	✓	✓	✓	✓	✓	✓	✓	✓	✓	
Spont. Reported Reactions and all AEs		✓	✓ ^F	✓	✓ ^F	✓	✓	✓ ^F	✓	
Changes in Tinnitus and/or Pain		✓ ^{J,D}	✓ ^{J,D}	✓ ^{J,D}	✓ ^{J,D}	✓ ^J	✓ ^{J,D}	✓ ^{J,D}	✓ ^J	✓ ^J
AEs of psychiatric status or withdrawal	✓	✓	✓	✓	✓	✓	✓	✓	✓	✓
Serious Adverse Events	✓	✓	✓	✓	✓	✓	✓	✓	✓	✓
Perception of Experimental Sessions						✓			✓	
Complete Stage 2 go to follow-up									✓	
RRPQ									✓	
Issue Memory Aid Card									✓	
Follow-up Questionnaire										✓
Termination Visit										✓

* If Visit 18 is more than 8 weeks after Visit 12, then subjects will need to repeat measures prior to starting Stage 2.

A = First session is one day after experimental session; B = Approximately six hours post MDMA; C = At the beginning of the session; D = As needed; E = Approximately every 60 minutes; F = Reactions collected for seven days post experimental session; G = All visits and Day 2 and Day 7 phone calls only; H = One month after the second experimental session but before the third experimental session; I = On the day of the third integrative session; J = Only in subjects with pre-existing tinnitus and/or chronic pain.

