9.2 Handling of Dropouts, Missing Data

Subjects who discontinue treatment prior to completing the second experimental session and the primary endpoint will be replaced. These dropout subjects will be asked to complete an outcome assessment prior to continuing to the long-term follow-up.

Early termination visit data for mITT and Safety variables will be analyzed at the closest scheduled visit after the last experimental session completed. If the closest visit has valid data, the early termination data will be assigned to the next available visit. If a subject discontinues and does not participate in an early termination visit, data from the last available visit will be used to replace the missing early termination visit data.

Partial or Missing Dates:

The following conventions will be used to impute missing portions of dates for adverse events and concomitant medications. Note that the imputed values outlined here may not always provide the most conservative date. In those circumstances, the imputed value may be replaced by a date that will lead to a more conservative analysis.

A. Start Dates

- 1) If the year is unknown, then the date will not be imputed and will be assigned a missing value.
- 2) If the month is unknown, then:
 - i) If the year matches the first dose date year, then impute the month and day of the first dose date.

- ii) Otherwise, assign 'January.'
- 3) If the day is unknown, then:
 - i) If the month and year match the first dose date month and year, then impute the day of the first dose date.
 - ii) Otherwise, assign the first day of the month.

B. Stop Dates

- 1) If the year is unknown, then the date will not be imputed and will be assigned a missing value.
- 2) If the month is unknown, then assign 'December.'
- 3) If the day is unknown, then assign the last day of the month.

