9.9.2.1 Secondary Efficacy Analyses at Secondary Endpoints

Assess 3 vs. 2 experimental MDMA sessions

For the CAPS, the absolute changes in the measure from the primary endpoint to end of Stage 1 for the 100 and 125 mg groups will be compared with t-tests. In the crossover subjects (40 mg) the absolute changes in the measures from the secondary (visit 27) endpoint to end of Stage 2 (visit 32) will be compared with t-tests.

Crossover Subject Analyses

CAPS data from subjects assigned to the 40 mg group in Stage 1, i.e. ‘crossover population,’ will be analyzed by t-tests on difference scores from primary endpoint (visit 12) in Stage 1 to secondary endpoint in Stage 2 (visit 27). Additionally, the following measures’ total scores will be analyzed in this same fashion: CAPS, PTGI, BDI-II, GAF, PSQI, DES-II, PDS.

Long-term Follow-up

For the CAPS, PDS, PTGI, BDI-II, GAF, PSQI, and DES-II, the absolute changes in the measures from baseline to the long-term follow-up visit (one year post final experimental year) will be compared with t-tests. The absolute changes in the measures from long-term follow-up to End of Stage 1 (visit 17, 100 mg and 125 mg) or long-term follow-up compared to End of Stage 2 (visit 32, 40 mg) will be compared with t-tests.

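### The Crossover population is defined by completing Stage 2 (visit 32) but is used for the visit 12 to visit 27 change, and SAP 9.1 and 9.9.2.1 describe it differently

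*SAP*

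**What the plan says.** SAP 9.1 lists four analysis populations. The third reads "Crossover: all subjects who completed Stage 2 in addition to completing Stage 1". It does not say what counts as completing Stage 2.

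SAP 9.9.2.1 applies that population by name in the crossover analysis. It begins with "CAPS data from subjects assigned to the 40 mg group in Stage 1", equates those subjects with the crossover population, and says the data "will be analyzed by t-tests on difference scores from primary endpoint (visit 12) in Stage 1 to secondary endpoint in Stage 2 (visit 27"). The same section identifies visit 32 as the close of Stage 2 when it sets out the comparison of three sessions with two: "from the secondary (visit 27) endpoint to end of Stage 2 (visit 32").

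The Stage 2 schedule in SAP 5.0 fixes the order of events. Its footnote on the visit 27 outcome measures reads "H = One month after the second experimental session but before the third experimental session".

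For subjects who stop, SAP 9.2 says "Early termination visit data for mITT and Safety variables will be analyzed at the closest scheduled visit". The Crossover population is not mentioned there. Protocol 5.4 asks that outcome evaluations be done after withdrawal where possible, and does not replace subjects who stop after the Stage 1 primary endpoint.

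On numbers, SAP 6.0 plans a "12:9:5 ratio between subjects in the active dose 1, active dose 2, and comparator dose treatment groups". Stage 2 is optional (Protocol 5.2.9), so five is the planned ceiling.

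**The concern.** The visit 12 to visit 27 contrast needs nothing later than visit 27. Under 9.1, however, membership is settled about two months later, at visit 32, after another drug session. A subject with CAPS measured at both visits who then declines the third session would be removed from an analysis whose data are complete. That is selection on an event after the outcome, and the subject's response by visit 27 may well influence whether the event occurs.

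The second text, in 9.9.2.1, has no completion condition. Two rules for one named population leave the analysis set open to choice once the data are known, in a document that SAP 2.0 presents as an a priori plan. At stake is the within-subject estimate of moving from 40 mg to an active dose, where each person is at least a fifth of the evidence.

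**Working it through.** **Step 1. Timing (Stage 2 schedule, SAP 5.0 and Protocol Table 3).** Visit 23 is the second Stage 2 session. Visit 27 comes one month after it and before visit 28, the third session. Visit 32 comes two months after visit 28.

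**Step 2. Who is in under each text.**

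| Comparator subject | SAP 9.1 | SAP 9.9.2.1 |
|---|---|---|
| Completes visit 32 | In | In |
| Visits 12 and 27 measured, stops before visit 32 | Out | In |
| Stops after one Stage 2 session, gives an early-termination CAPS | Out | In, if 9.2 allows that value to stand at visit 27 |
| Never enters Stage 2 | Out | In by the wording, but with no visit 27 value |

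Only in the first row do the two texts plainly give the same result.

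**Step 3. The plan's own figures.** The documents give no power or precision for the crossover analysis. The power figure that they do give, in Protocol 12.1, is 0.33 for 18 versus 5 at an effect size of 0.8. It reproduces with a two-sided two-sample t-test: df = 21, noncentrality = 0.8 × √(18 × 5/23) = 1.58, power 0.327. It concerns the randomized comparison and says nothing about Stage 2.

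**Step 4. Effect of losing one of five on the mean.** The documents give no CAPS change SD and no Stage 2 drop-out rate. Assume five independent changes, normal with mean -20 and SD 20 (negative is improvement). The expected largest of five standard normal values is ∫5zφ(z)Φ(z)⁴dz = 1.163, so the least improved subject has expected change -20 + 20 × 1.163 = 3.26 and the most improved -20 - 23.26 = -43.26.

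- Lose the least improved: (5 × -20 - 3.26)/4 = -25.8.
- Lose one at random: -20.0.
- Lose the most improved: (5 × -20 + 43.26)/4 = -14.2.

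**Step 5. Effect on the test (one-sample t on changes, two-sided 0.05).** With all five, the standardized mean is 20/20 = 1, noncentrality √5 = 2.24, critical value 2.776, power 0.40. With a random four, noncentrality is √4 = 2, critical value 3.182, power 0.29. The two selective cases come from 200,000 simulated sets of five: 0.58 with the least improved removed and 0.27 with the most improved removed.

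**Step 6. A check without a distribution.** If k of five are dropped, completers' mean minus all-five mean = (k/5) × (completers' mean - mean of those dropped). With one dropped and completers at -30:

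- dropped subject at 0: shift (1/5)(-30 - 0) = -6, an overstatement of 6 points;
- at -30: no shift;
- at -45: (1/5)(-30 + 45) = +3, an understatement of 3 points.

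**Step 7. An illustration of p-values.** Completers change by -15, -25, -35 and -45: mean -30, t = -4.65, p = 0.019. Adding a fifth subject at +5 gives mean -23, t = -2.67, p = 0.056. Adding one at -30 gives mean -30, t = -6.00, p = 0.004. One person can move the result across 0.05, and keeping that person can strengthen or weaken it.

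**The case against.** The strongest reply is that the section specifying the analysis takes everyone assigned to 40 mg, so a measured visit 27 CAPS would be kept and 9.1 is only loose wording. The undefined term in 9.1 adds some force: Protocol 5.4 keeps certain subjects in follow-up after treatment stops, so stopping treatment need not mean failing to complete. This bars the claim that the analysis will certainly drop such subjects. It does not remove the problem, because 9.9.2.1 names the population that 9.1 defines, and the two do not match.

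A reader might infer that the definition favours the active dose. The documents do not support that. They give no drop-out rate or reasons, and the sign depends on who stops. A subject who improves and declines a third session biases the estimate the other way, and losing a subject at random lowers power.

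A reader might also infer that drop-outs would be hidden. SAP 9.6 tabulates discontinuations with reasons by treatment group, and 9.7 describes the mITT population as well as Crossover. Nor can it be said that Stage 1 is firmly protected by mITT, since SAP 9.9.1 names no population for the primary analysis.

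On early termination, a comparator subject who reached Stage 2 with a visit 12 assessment is also in mITT, so 9.2 can be read as placing that subject's CAPS at visit 27. The text is unclear, but it does not exclude the value.

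Finally, this is an open-label, uncontrolled analysis of at most five planned subjects in a pilot. Protocol 12.0 calls it exploratory, although the SAP lists it among secondary analyses. That limits the stakes and stands.

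**Conclusion.** The point holds as a conflict of definitions with a real consequence. Followed as written, 9.1 discards measured visit 27 outcomes because of a later event that the visit 12 to visit 27 question does not need, and the differing description in 9.9.2.1 contradicts 9.1 without repairing it.

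Under the assumed normal changes, losing one of five puts the expected mean anywhere from -14.2 to -25.8 around a true -20, and the chance of significance from 0.27 to 0.58 around 0.40. The ends of these ranges are extreme cases, in which the subject lost is always the most or the least improved. Overstatement is the likelier direction if subjects stop for non-response or intolerance, but the documents do not establish why they would stop. If nobody stops in Stage 2, the result does not change. The randomized comparison at visit 12 is unaffected in every case.

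**What to change.** In SAP 9.1, define the set for the visit 12 to visit 27 analysis separately for each measure: all comparator subjects who received one or more Stage 2 experimental sessions and have a Stage 2 value of that measure at visit 27 or at early termination. Assign early-termination values to the closest Stage 2 endpoint, and say in 9.2 that this rule covers Stage 2. The definition should be by measure because the PDS is also collected after the first Stage 2 session; a general requirement for any Stage 2 outcome could admit a subject with a PDS score but no Stage 2 CAPS.

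Report the number who entered Stage 2 without a usable value. Restrict the visit 27 to visit 32 contrast to subjects with both values. Keep Stage 2 completers as a sensitivity set. Reword 9.9.2.1 to match.

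The cost is a few sentences of SAP text and no new data. The downside is that the Stage 2 estimate may change and could be less favourable.

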9.2 Handling of Dropouts, Missing Data

Subjects who discontinue treatment prior to completing the second experimental session and the primary endpoint will be replaced. These dropout subjects will be asked to complete an outcome assessment prior to continuing to the long-term follow-up.

Early termination visit data for mITT and Safety variables will be analyzed at the closest scheduled visit after the last experimental session completed. If the closest visit has valid data, the early termination data will be assigned to the next available visit. If a subject discontinues and does not participate in an early termination visit, data from the last available visit will be used to replace the missing early termination visit data.

Partial or Missing Dates:

The following conventions will be used to impute missing portions of dates for adverse events and concomitant medications. Note that the imputed values outlined here may not always provide the most conservative date. In those circumstances, the imputed value may be replaced by a date that will lead to a more conservative analysis.

A. Start Dates

- 1) If the year is unknown, then the date will not be imputed and will be assigned a missing value.
- 2) If the month is unknown, then:
 - i) If the year matches the first dose date year, then impute the month and day of the first dose date.

- ii) Otherwise, assign 'January.'
- 3) If the day is unknown, then:
 - i) If the month and year match the first dose date month and year, then impute the day of the first dose date.
 - ii) Otherwise, assign the first day of the month.

B. Stop Dates

- 1) If the year is unknown, then the date will not be imputed and will be assigned a missing value.
- 2) If the month is unknown, then assign 'December.'
- 3) If the day is unknown, then assign the last day of the month.

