9.8 Prior and Concomitant Medications

The number and percent of subjects who took medications prior to and after signing informed consent will be summarized descriptively for each treatment group. Concomitant medications will be summarized similarly. Prior and concomitant medications will be summarized for the Safety Population. Psychiatric medications will be coded to common drug classes and terms.

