9.9.4 Safety Analyses

The primary measure of safety will be the reporting of adverse events. The Adverse events considered are Treatment Emergent Adverse Events (TEAE) defined as those AE's that occurred after dosing and existing medical history diagnoses that worsened during the study. Verbatim terms on case report forms will be mapped to preferred terms and system organ classes using the MedDRA dictionary. For incidence reporting if a subject has more than one AE mapped to the same preferred term, that AE will be reported only once using the highest severity and closest relationship to study drug. Subject incidence of AEs will be displayed by Stage I treatment group and by system organ class. AEs will also be summarized by severity and relationship to study drug. Subject incidence of SAEs by Stage I treatment group will also be displayed. In addition to the listing of all AEs, a listing of SAEs and a listing of AEs leading to discontinuation of study drug will be included.

Summary tables of frequency listings of commonly reported AEs (Spontaneously Reported Reactions) mapped to preferred terms will be displayed during and after each experimental session by Stage 1 treatment group.

Columbia Suicide Severity Rating Scale (C-SSRS)

Suicidal ideation and behavior will be summarized according to suggestions made in the Columbia-Suicide Severity Rating Scale Scoring and Data Analysis Guide [2]. A positive response for suicidal ideation is counted when a subject answers "yes" to any one of the five suicidal ideation questions (Categories 1-5) on the C-SSRS, i.e. a score > 0 for suicidal ideation score. Serious suicidal ideation is a suicidal ideation score of 4 or 5. A positive response for suicidal behavior occurs when a subject answers "yes" to any one of the five suicidal behavior questions (Categories 6-10) on the C-SSRS, i.e. a score > 0 for suicidal behavior score. The number and percent of positive responses of Positive Ideation, Serious Ideation, and Positive Behavior will be tabulated by Stage I treatment group and time period. Compare lifetime serious suicidal ideation and positive behavior frequencies to cumulative frequencies anytime during the study until end of Stage 1 and Stage2.

Subjective Units of Distress (SUD)

Descriptive statistics for SUD scores will be calculated by Stage 1 treatment group and time period with counts and percentages.

Visual analog scale for Tinnitus and/or Pain visual analog scale

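### SAP 9.2 imputes partial start dates to the first dose without checking the stop date, so a pre-dose adverse event can become treatment-emergent and a pre-study drug can lose its prior-use status

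*SAP*

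**What the plan says.** The date conventions in SAP 9.2 cover both AEs and concomitant medications. For start dates:

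- Month unknown: "If the year matches the first dose date year, then impute the month and day of the first dose date". In any other year, January is assigned.
- Day unknown: "If the month and year match the first dose date month and year, then impute the day of the first dose date". In any other month: "Otherwise, assign the first day of the month".
- Year unknown: the date stays missing.

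Unknown stop dates go late, to December or to the last day of the month. No rule relates the imputed start to the stop. Later sessions and the first Stage 2 dose are not used, and the first dose date is not defined by stage. SAP 9.2 concedes that its values may not be the most conservative ones, and adds that "the imputed value may be replaced by a date that will lead to a more conservative analysis".

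Three planned outputs use these dates or could use them. SAP 9.9.4 defines treatment-emergent AEs as those after dosing (plus worsened medical history) and shows incidence by Stage 1 group. It also says that spontaneously reported reactions "will be displayed during and after each experimental session by Stage 1 treatment group". SAP 9.8 summarises "subjects who took medications prior to and after signing informed consent".

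**The concern.** Anchoring to the first dose is a familiar convention for an AE of uncertain onset, because it keeps a possibly drug-related event in the treatment-emergent count. It makes sense only while the event could have begun after dosing. Where the stop date shows that the event was over before session 1, the imputed interval is impossible and the classification is false.

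For medications the convention has no such purpose. SAP 9.8 splits use at consent, which precedes the first dose by weeks, so moving an uncertain start forward to the first dose can put a pre-study drug on the wrong side of the split.

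The design also has more than one dosing date: three sessions in the active groups, and up to five in comparator subjects who cross over. A rule that knows only the first will misplace the onset of later events.

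**Working it through.** The plan states no figure on this point, so there is none to reproduce. The check applies the SAP 9.2 rules as written. Calendar dates below are illustrative.

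**1. AE that ended before session 1.** Protocol 8.5 collects SAEs, events needing medical attention and psychiatric AEs before any dose, and Protocol 4.1 puts session 1 three to five weeks after enrolment. Take consent on 18 August 2014, enrolment on 8 September and first dose on 6 October (28 days after enrolment).

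- Start recorded only as 2014, resolved 19 September: imputed start 6 October, 17 days after the stop.
- Start recorded as October 2014, resolved 3 October: imputed start 6 October, 3 days after the stop.

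Both count as treatment-emergent if a start on the first-dose date qualifies. SAP 9.9.4 gives no same-day rule, so that is an assumption. At the planned group sizes in SAP 6.0 (12, 9 and 5), one subject wrongly counted adds 1/12 = 8.3, 1/9 = 11.1 or 1/5 = 20 percentage points to that group's incidence of the term.

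**2. Drug tapered off before session 1.** Protocol 5.2.1 and 9.0 record pre-study medication at screening and require psychiatric drugs to be tapered before session 1. With the same dates, take a pre-study drug whose start is recorded only as 2014 and whose last use was 22 September. The imputed start is 6 October, which is 14 days after the stop and 49 days after consent. A derivation based on start date omits it from the prior-use count. The error needs the start year to equal the first-dose year; an earlier year gives January of that year.

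**3. Day unknown, event after a later session.** Let the session fall on day 1 to 30 of a 30-day month and onset be 0 to 7 days later, all equally likely (30 × 8 = 240 cases). The imputed 1st precedes the session when onset is in the same month and the session is not itself on the 1st. For lag k that is 29 − k days. Summed over k = 0 to 7: 8 × 29 − 28 = 204, and 204/240 = 85%. Running the rules over every first-dose day of a year also gives 85%, with a mean shift of about 15 days. No Stage 2 event goes back to the first dose in this case.

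**4. Month unknown, Stage 2 event in a crossover subject.** It goes to the first 40 mg session if it falls in the first-dose calendar year. With first dose uniform over the year and mean onset 3.5 days after the session, the share is about 1 − (offset + 3.5)/365. Offsets in days come from Protocol 4.1, 5.2.3, 5.2.7 and Table 3, with gaps filled by assumption:

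| Visit spacing | Offsets, Stage 2 sessions 1-3 | Share dated to first 40 mg session |
|---|---|---|
| Middle | 95, 123, 153 | 73%, 65%, 57% |
| Shortest | 45, 66, 82 | 87%, 81%, 77% |
| Longest | 236, 271, 315 | 34%, 25%, 13% |

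Example: first dose 10 February 2014 (40 mg), Stage 2 session 1 on 16 May, event on 18 May. Day unknown gives 1 May; month unknown gives 10 February. Counterexample: first dose 6 October 2014, event 12 January 2015, month unknown. This gives January 2015, not the first dose.

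**5. Which outputs change.** In steps 3 and 4 every imputed date is the first dose date or later, so the event stays treatment-emergent. Incidence is shown by Stage 1 group, so it stays in the same column. Only steps 1 and 2 change a planned classification.

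**The case against.** The strongest reply has four parts.

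- *The first-dose anchor is deliberately conservative, and SAP 9.2 allows a better date where it is not.* The first half is sound for an AE whose stop date leaves post-dose onset possible, and that use should stay. The override is permissive, has no criterion and does not say which direction is conservative. Counting a pre-dose AE as treatment-emergent could itself be called conservative, so the clause does not reliably correct step 1. The therapists and subject also know the dose from Visit 12.
- *Known stop dates settle medication status without the start.* A drug stopped before consent was plainly not taken after it. That stands for a careful programmer, but SAP 9.2 does not say that the stop date prevails. It also does not help a drug that was started before consent and tapered off after it.
- *The by-session table is hardly exposed.* Reactions are collected during the session and by daily contact for seven days, on their own CRF page (Protocol 5.1.2, 5.2.5, 8.2). The session is then known without the date, and a partial date is unlikely. This largely stands, although the SAP does not say that the session comes from the CRF. Partial dates are more plausible for pre-study drug histories and for events recalled at the 12-month visit with memory cards that are not collected.
- *The 85% assumes onset within the daily-contact window, where dates are best recorded.* That is right. It describes what the rule does to a partial date, not how often one occurs.

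A reader might infer more: that the rule moves active-dose events into the 40 mg period and so narrows the apparent dose difference. The documents do not support this. AE and SAE incidence is tabulated by Stage 1 group, so a crossover subject's Stage 2 event is in the 40 mg column whatever its date.

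**Conclusion.** The concern holds on the missing stop-date check and on applying the first-dose anchor to medications. As written, SAP 9.2 can produce a start later than the stop, turn a pre-dose AE into a treatment-emergent one, and misstate prior medication use in SAP 9.8. These results need a partial start in the first-dose year or month, a first-dose-date start counted as treatment-emergent, and prior use derived from the start date.

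The misdating around later sessions is real but secondary. About 85% of day-unknown events would be dated before their own session, under uniform session days and onset 0-7 days later. From 13% to 87% of month-unknown Stage 2 events would be dated to the first 40 mg session, depending on visit spacing and on which Stage 2 session they follow. This affects onset dates and any session-level or stage-level reading. It does not affect treatment-emergent status or the AE tables by Stage 1 group, and there is no basis for saying that it biases the planned dose comparison.

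The documents do not say how many dates are partial, so the number of affected records is unknown and may be small. The point is worth correcting because the rule gives wrong answers in foreseeable cases and the correction is cheap.

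**What to change.** Amend SAP 9.2 as follows.

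1. Never impute a start later than the known or imputed stop date. Class an AE whose stop date precedes the first dose as not treatment-emergent.
2. For medications, impute the earliest date compatible with the known parts (1 January, or the 1st of the month) instead of the first dose date.
3. For AEs and reactions after session 1, take the session from the CRF page or visit at which the event was recorded. Where the known date parts allow, impute a date no earlier than that session. Using the known month alone would not do, because sessions 21 to 29 days apart can share a month.
4. Replace the sentence permitting a more conservative date with these rules.

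The cost is a few lines of SAP text and derivation code, with no new data. Two limits remain. A drug truly started after consent but with only the year known may be counted as prior use. An AE first reported at a later visit may still be given the wrong session, so such records should be flagged in the listing.
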